2.1.2 Secondary Objectives

The secondary objectives of the study are to:

- To assess the risk factors for each of the following outcomes: DSA formation; IA; transplant glomerulopathy (TG); acute and chronic forms of antibody-mediated rejection (ABMR); C1q-binding DSA; HLA-DQ DSA; DSA IgG₃ isotype; requirement for and type of antibody reduction required; various threshold levels of estimated glomerular filtration rate (eGFR) (less than 30, 40, and 50 mL/min/1.73 m²); and the four components of the traditional composite endpoint, consisting of graft loss, mortality, biopsy-proven acute rejection (BPAR), and loss to follow-up; and additionally, the persistence of DSA and IA.
- Assess and compare, between treatment groups, the association/correlation of the appearance of DSA with the development of IA on molecular profiling.
- Compare, between treatment cohorts, the incidence and hazards of each of the following, occurring over the course of one year and, where appropriate, at 24 months post-transplantation: DSA, HLA-DQ DSA, C1q-binding DSA, DSA IgG₃ isotype, IA, TG, select BANFF histology grades (acute and chronic forms of ABMR, acute and chronic active TCMR, borderline changes, and IFTA), graft loss, mortality, and BPAR.
- Compare between cohorts the incidence of various thresholds of eGFR (less than 30, 40, 50 mL/min/1.73 m², and a five-point decline).
- Compare the distribution of ordinal categories of antibody strength (weak, moderate, strong) between treatment groups across the study time course as well as at each time point.
- Compare raw MFI scores between treatment groups at each time point and across the duration of the study.
- Examine and compare histopathology between the treatment cohorts in biopsies obtained for cause and for maintenance during the course of clinical care.
- Examine and compare outcomes as a function of tacrolimus manufacturer and the number of switches between immediate-release tacrolimus products.
- Summarize AEs between study groups.
- Compare the change in eGFR over the study duration beginning from 30 days post-transplant between groups, and in patients who develop DSA or IA.

- Compare the persistence of the development of IA on molecular profiling between the two cohorts across the study duration in those patients who develop IA on molecular profiling.

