3.1.2 Secondary Objectives

The secondary objectives of the study, as stated in the protocol, have been further clarified and adjusted to more closely address the research questions and in consideration of data availability. They are to:

- Assess the risk factors for each of the following outcomes: Interstitial Fibrosis and Tubular Atrophy (IFTA), IFTA and Inflammation, biopsy-proven acute rejection (BPAR), the four-part traditional composite endpoint, early mycophenolate mofetil (MMF) interruption/discontinuation, and estimated glomerular filtration rate (eGFR) status based on three thresholds 30, 40, and 50 at one year.
- Assess and compare, between treatment groups, the association/correlation of the appearance of DSA with the development of IA on molecular profiling at one year.
- Assess and compare, between treatment groups, the incidence of each of the following, occurring over the course of one year : De novo DSA, C1q-binding DSA, DSA IgG₃ isotype, IA, transplant glomerulopathy (TG), select BANFF histology grades (acute and chronic forms of antibody-mediated rejection (ABMR), acute and chronic active T-cell mediated rejection (TCMR), borderline changes, and IFTA), graft loss, mortality, and BPAR.
- Compare, between treatment groups, the incidence of various thresholds of eGFR (less than 30, 40, 50 mL/min/1.73 m²) at Day 365 visit and a five-point decline from Day 30 to Day 365).
- Summarize the distribution of ordinal categories of antibody strength (weak, moderate, strong) between treatment groups across the 1-year study time course.
- Summarize maximum Mean Fluorescence Intensity (MFI) scores by treatment group across the duration of the study.
- Examine histopathology in cases where biopsies were taken for maintenance (up to fourteen months) between treatment groups. In cases where biopsies were performed for cause, they will be examined separately.
- Summarize tacrolimus manufacturer and the number of switches between immediate-release tacrolimus products by the occurrence of study composite endpoint.
- Summarize tacrolimus manufacturer and the number of switches by the status of renal dysfunction.
- Summarize adverse events (AEs) between treatment groups.

- Summarize the absolute and percent changes in eGFR over the study duration beginning from 30 days post-transplant between groups, and in subjects who develop DSA or IA.

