4 SAMPLE SIZE

The sample size for this study was determined based upon a comparison of the rate of the two-part composite endpoint in the Astagraf XL group compared to the immediate-release tacrolimus group. Assuming a rate of 20% would be observed for the immediate-release tacrolimus group compared to a rate of 10% for the Astagraf XL group, 220 subjects per group are needed to achieve an 80% power to detect a difference between Astagraf XL and immediate-release tacrolimus with a two-sided alpha level of 0.05. The study will enroll 275 subjects/group (550 total) to allow for 20% dropout.

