9. IFTA
10. IFTA and Inflammation (IFTA and ci $>$ 0)
11. Acute and chronic forms of ABMR
12. eGFR at various thresholds (less than 30, 40, 50 mL/min/1.73 m² at one year; and a five-point decline from Day 30 to Day 365)
13. Graft loss
14. Mortality

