15. BPAR

16. The four-part traditional composite endpoint

Separate risk factor analyses will be conducted for BID Immediate-release Tacrolimus treatment group only. Manufacturer will be included as additional covariate.

Ordinal assessments of antibody peak strength (weak, moderate, and strong) will be summarized based on the results over the course of one year using frequencies and percentages. Analysis of treatment group difference will be done using Fisher's Exact Test.

The continuous endpoint of Peak MFI score will be summarized with descriptive statistics based on the results over the course of one year by antibody.

Histopathology assessments will be summarized with both descriptive statistics and frequencies and percentages. Raw biopsy scores, including g, t, v, i, cg, ct, ci, cv, ah, ptc, and mm will be summarized as ordinal outcomes. Analysis of treatment group differences will be performed using Fisher's Exact Test. The incidence of binary outcomes including ci, ct, and ptc scores greater than 1 will be summarized with frequencies and percentages. Analysis of treatment group differences will be performed using Fisher's Exact test.

Assessments of association between De novo DSA and IA will be analyzed with logistic regression models using DSA formation as the response and IA as predictor using the same covariates detailed in Section 7.4.1.1.

Mean of eGFR by treatment group will be plotted across visits.

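### The SAP describes continuous eGFR but never compares it between arms: every between-arm eGFR test is on a yes/no variable, although the protocol made comparison of change a secondary objective.

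*SAP*

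**What the plan says.** - **Protocol 2.1.2** lists as a secondary objective: "Compare the change in eGFR over the study duration beginning from 30 days post-transplant between groups, and in patients who develop DSA or IA". Protocol 2.3.2 adds that eGFR will be assessed over time.
- **Protocol 7.4.2** gives a method for continuous eGFR change only in patients who develop IA or DSA, starting at diagnosis. It uses the mixed repeated-measures model set out for MFI, which works on rank scores. No method is given for the all-patient comparison.
- **SAP 3.1.2** says in general terms that the objectives were clarified and adjusted, partly because of data availability. The eGFR objective now reads: "Summarize the absolute and percent changes in eGFR over the study duration beginning from 30 days post-transplant between groups".
- **SAP 7.4.2** tests eGFR by logistic regression on values below 30, 40 and 50 at one year, "and a five-point decline from Day 30 to Day 365". For continuous eGFR it says only: "Mean of eGFR by treatment group will be plotted across visits".
- **SAP 6.5 and 7.5.2** define the Day 30 value as the eGFR baseline. For biochemistry, 7.5.2 plans descriptive statistics and within-subject change by visit, in the safety set.
- **SAP 7.1** cancels regression for any outcome with an event rate below 10%.
- **SAP 8**, the revision history, has nine entries. None covers the change in the eGFR objective.

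**The concern.** A stated secondary objective has lost its comparison, and no reason specific to eGFR is given. Where SAP 7.3.2 drops the planned compliance comparisons, it says so and says why. Lack of data is not an obvious reason here. SAP 6.1.2 derives eGFR thresholds at months 1, 3, 6, 9 and 12, and SAP 7.4.2 plots means across visits, so the values are expected to exist.

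A yes/no cut discards how far each patient lies from the cut. Each tested outcome also uses only one or two of the five scheduled first-year values. The trial calls itself exploratory, so its readers mainly need estimates. As planned, they would get odds ratios for crossing a cut, but no stated between-arm difference in mL/min/1.73 m² with its precision.

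**Working it through.** **The plan's own figure.** SAP 4 says "220 subjects per group are needed to achieve an 80% power", at a "two-sided alpha level of 0.05", for 20% against 10% on the composite endpoint. The two-proportion formula with continuity correction gives 219 (199 without). Exact Fisher power at 220 per group is 0.811. Dropout: 220/0.80 = 275, as stated. This reproduces, but it concerns the composite. No figure is given for eGFR.

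**Assumed inputs for eGFR.** None of these is in the documents: one-year control mean 55, SD 18 (range 15-20), true difference 5 mL/min/1.73 m², Day 30 to Day 365 correlation r of 0.5-0.7. For the five-point fall, control mean change is taken as zero and the difference is taken to arise wholly after Day 30. From SAP 4: n = 220 per arm, two-sided 0.05.

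**Continuous Day 365 value.** SE = 18 × √(2/220) = 1.716. Power = Φ(5/1.716 − 1.96) = Φ(0.95) = 0.83.

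**Thresholds.** The event rate in each arm is Φ((cut − mean)/18), with means 55 and 60. Power is then the usual two-proportion formula.

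**Five-point fall.** SD of change = 18 × √(2(1 − r)), which is 18.0 at r = 0.5 and 13.9 at r = 0.7. The rates are Φ(−5/SD) and Φ(−10/SD).

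| Outcome | Control rate | Astagraf XL rate | Power |
|---|---|---|---|
| Day 365 eGFR, continuous | – | – | 0.83 |
| Below 50 | 0.391 | 0.289 | 0.61 |
| Below 40 | 0.202 | 0.133 | 0.49 |
| Below 30 | 0.082 | 0.048 | 0.31 |
| Five-point fall, r = 0.5 | 0.391 | 0.289 | 0.61 |
| Five-point fall, r = 0.7 | 0.360 | 0.237 | 0.81 |
| Same change, continuous, r = 0.5 | – | – | 0.83 |
| Same change, continuous, r = 0.7 | – | – | 0.96 |

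**The 10% bar.** The pooled rate below 30 is (0.082 + 0.048)/2 = 0.065, so this outcome would get no regression and its 0.31 is the power of a test that would not be run. Over SD 15-20 the pooled rate is 3.5-8.6%, always under the bar.

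**Sensitivity to SD, difference 5.** For SD 15 to 20, continuous power runs from 0.94 to 0.75. Below 50 gives 0.76 to 0.53, below 40 gives 0.57 to 0.44, and below 30 stays near 0.30.

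**Sensitivity to the difference.** At a true difference of 3 and SD 18, continuous power is 0.42, against 0.27, 0.22 and 0.15 for the cuts at 50, 40 and 30. The five-point fall gives 0.27-0.41, against 0.42-0.62 for continuous change. All powers fall; the continuous analysis still leads.

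**Why the direction does not depend on these inputs.** For a small shift in a normal outcome, a cut at event proportion p keeps φ(z_p)²/(p(1 − p)) of the information: 34% at p = 0.10, 49% at 0.20, 62% at 0.40 and at most 64% at 0.50.

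**The case against.** The strongest reply has four parts.

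1. **eGFR is not ignored.** A reader of SAP 7.4.2 alone might infer that continuous eGFR is reduced to a plot. The documents do not support that: SAP 3.1.2 plans absolute and percent change from Day 30, and SAP 7.5.2 plans by-visit summaries and change. By-arm means and SDs will therefore be available. What is missing is a stated contrast with a confidence interval. SAP 7.4.2 has no method line for the 3.1.2 summary, and the 7.5.2 tables use the safety set, grouped by treatment received.

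2. **Change is already tested.** The five-point fall does test it, crudely. At r = 0.7 its power (81%) nearly matches the unadjusted continuous Day 365 comparison (83%). The like-for-like comparator is continuous change, at 96%.

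3. **The protocol promised less than it seems.** A reader might infer that the SAP removed an all-patient mixed model, or invented the thresholds. Neither holds. The protocol's model covered only IA/DSA patients, on rank scores, so it would not have given a difference in mL/min/1.73 m² either. The thresholds are protocol endpoints. The all-patient comparison was an objective without a method.

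4. **The data are imperfect.** Creatinine is recorded as obtained under standard of care, eGFR is calculated where available (Protocol 5.3.9), and clinical data collection largely stops at discontinuation, which includes graft loss and death (Protocol 6.1). This stands, but it affects the thresholds equally: SAP 7.10.1 does not impute missing eGFR endpoints.

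The trial is also sized only on the composite and does not adjust for multiplicity, which limits the weight of any secondary test. That argues for estimation, not against it.

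**Conclusion.** The point holds in this form: continuous eGFR is described but never compared between arms, although the protocol made comparison of change a secondary objective, and the SAP does not explain the downgrade. It should be corrected, but it does not touch the primary endpoint.

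Under the assumed inputs the loss is roughly 20 to 35 percentage points of power for the cuts at 50 and 40 (83% against 61% and 49%), and about 15 to 20 points for change (83-96% against 61-81%). The cut at 30 would probably get no regression at all. These sizes rest on an assumed mean, SD, difference and correlation. The direction rests on the information lost by any cut of a roughly normal outcome.

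A reader might also infer that repeated measures would raise power for the Day 365 difference itself. In a model with unstructured covariance, treatment-by-visit and Day 30 as an outcome, complete data without baseline covariates give the same Day 365 difference and standard error as a two-sample comparison. Any gain comes from baseline covariates and from patients with partly missing values.

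**What to change.** Add to SAP 7.4.2 a repeated-measures model of eGFR at Days 30, 90, 180, 270 and 365 in the mFAS:

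- Terms: treatment, visit, treatment-by-visit, the stratification factors, and recipient age, sex and race, with unstructured covariance.
- Report the between-arm Day 365 difference and the between-arm difference in change from Day 30 to Day 365, each with a 95% confidence interval.
- Keep Day 30 as an outcome. It follows randomisation, so conditioning on it could remove an early treatment effect. A Day 30-adjusted analysis can be supportive if wanted.
- Keep the three thresholds and the five-point fall as supportive.
- State one rule for eGFR after graft loss or death and apply it to both the continuous and the threshold analyses. The choice is between treating such values as unobserved, which describes function while the graft works, and assigning a fixed low value that also counts as below every threshold.
- Add a line to SAP 8 recording the change to the eGFR objective.

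Cost: SAP wording, one standard model on values already derived for the plot, and one more secondary comparison without multiplicity adjustment. No new data are needed.

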7.4.3 Analysis of Exploratory Endpoints

Analysis will be performed on the secondary composite endpoint consisting of DSA formation and the presence of TG ($cg > 0$). Logistic model with the same covariates of the primary analysis will be conducted for treatment group differences with the incidence of DSA or TG as the response and treatment group as the predictor. The analysis will be performed using the biopsy analysis set.

7.4.4 Analysis of Other Variables

Not applicable

7.5 Analysis of Safety

All analysis of safety will be presented by treatment group for SAF, unless specified otherwise.

7.5.1 Adverse Events

The coding dictionary for this study will be MedDRA. All AEs will be summarized by SOC and PT.

The following lists the TEAE summaries that will be provided:

- Number of TEAEs,
- Number and percentage of subjects with TEAEs,

- Number and percentage of TEAEs by relationship,
- Number and percentage of subjects with TEAEs by relationship,
- Number and percentage of TEAEs by intensity,
- Number and percentage of subjects with TEAEs by intensity,
- Number and percentage of TEAEs occurring in at least 3.5% of any treatment group,
- Number and percentage of subjects with TEAEs occurring in at least 3.5% of any treatment group,
- Exposure adjusted incidence rate (EAIR) of TEAEs,
- Number of TEAEs leading to permanent discontinuation of study drug,
- Number and percentage of subjects with TEAEs leading to permanent discontinuation of study drug,
- Number of serious TEAEs,
- Number and percentage of subjects with serious TEAEs,
- Number and percentage of serious TEAEs by relationship,
- Number and percentage of subjects with serious TEAEs by relationship,
- Exposure adjusted incidence rate (EAIR) of serious TEAEs,
- Number of deaths.

The number and percentage of subjects with TEAEs, as classified by PT only, will be summarized for each treatment group.

If a TEAE has missing grade of intensity or relationship, the highest level of assessment, i.e. Severe for intensity and Probable for relationship, will be used for the table summary. The data listings will still present original missing assessments.

7.5.2 Clinical Laboratory Evaluation

The baseline renal function (serum creatinine, eGFR) will be defined as the value measured at the Day 30 visit. For all other data, the baseline value will be defined as the last observation collected prior to reperfusion of the transplanted kidney.

Quantitative clinical laboratory variables, i.e. hematology and biochemistry, will be summarized using mean, standard deviation, minimum, maximum and median for each treatment group at each visit. Additionally, a within-subject change will be calculated as the post-baseline measurement minus the baseline measurement and summarized in the same way.

Urinalysis and coagulation results will be presented in data listing.

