1.3 Summary of Key Safety Information for Study Drugs

As with other potent immunosuppressive agents, patients receiving tacrolimus are at an increased risk for infections (viral, bacterial, fungal, and protozoal). Likewise, the course of pre-existing infections may be aggravated. Overall, infections have been reported frequently in patients being treated with tacrolimus. Both generalized and localized infections can occur. Patients receiving immunosuppressive agents are also at an increased risk of developing malignancies, particularly of the skin. Benign as well as malignant neoplasms, including Epstein-Barr virus (EBV)-associated lymphoproliferative disorders, have been reported in association with tacrolimus treatment.

Tacrolimus can result in renal function impairment in post-transplant patients due to its vasoconstrictive effect on renal vasculature. Acute renal impairment, that is usually reversible, can result in high serum creatinine, hyperkalemia, decreased secretion of urea, and hyperuricemia.

Additional adverse reactions reported in patients receiving tacrolimus include allergic and anaphylactoid reactions, ventricular hypertrophy or hypertrophy of the septum (reported as cardiomyopathies; most cases have been reversible), encephalopathies (such as posterior reversible encephalopathy syndrome [PRES], and pure red cell aplasia [PRCA]). In the case of PRCA, all patients reported risk factors such as parvovirus B19 infection, underlying disease, or concomitant medications associated with PRCA. Gastrointestinal perforation has also been reported in patients treated with tacrolimus, although all cases were considered a complication of transplant surgery or accompanied by infection, diverticulum, or malignant neoplasm. Tacrolimus may prolong the QT interval and may cause Torsade de Pointes.

For additional information regarding possible adverse drug reactions related to tacrolimus or Astagraf XL, please refer to the Package Inserts (PIs) for Astagraf XL or the various immediate-release tacrolimus products.

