7.5.2 Laboratory Assessments

For quantitative laboratory measurements obtained during standard of care, descriptive statistics will be used to summarize results and change from baseline by treatment group and time point. Shifts relative to normal ranges from baseline to each time point during the

treatment period with regard to lab tests will also be tabulated. Laboratory data will be displayed in listings.

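### The SAP omits the protocol's normal-range laboratory shift tables, leaving no by-arm out-of-range count for potassium, glucose, urea nitrogen, sodium or blood counts

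*SAP*

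**What the plan says.** Protocol 7.5.2 (Laboratory Assessments) plans four things for laboratory data recorded under standard of care. Two are summaries: "descriptive statistics will be used to summarize results and change from baseline by treatment group and time point". The third is a table of categories: "Shifts relative to normal ranges from baseline to each time point during the" treatment period are to be tabulated. The fourth is listings.

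SAP 7.5.2 (Clinical Laboratory Evaluation) keeps the summaries. Haematology and biochemistry "will be summarized using mean, standard deviation, minimum, maximum and median for each treatment group at each visit", and in addition "a within-subject change will be calculated as the post-baseline measurement minus the baseline measurement and summarized in the same way". It contains no normal-range category. It also states: "Urinalysis and coagulation results will be presented in data listing". The only threshold table in the SAP's laboratory safety section is 7.5.2.1, for ALT, AST, ALP and total bilirubin.

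The SAP uses two baselines. For kidney function: "The baseline renal function (serum creatinine, eGFR) will be defined as the value measured at the Day 30 visit". For the rest: "For all other data, the baseline value will be defined as the last observation collected prior to reperfusion of the transplanted kidney".

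On the risks at issue, Protocol 1.3 says of tacrolimus-related kidney effects: "Acute renal impairment, that is usually reversible, can result in high serum creatinine, hyperkalemia, decreased secretion of urea, and hyperuricemia". Protocol 1.2.2 lists abnormal glucose metabolism among the clinically important events seen with Prograf.

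**The concern.** Laboratory harm usually shows as a minority of patients leaving the normal range. A mean moves little when that happens, and a minimum or maximum shows one patient. A shift table shows how many patients in each arm went out of range, and in which direction. The protocol promised one, and the SAP does not carry it forward.

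The omission is also easy to miss. The SAP describes itself as an elaboration of the protocol's analysis, and both documents require the study report to justify departures from the SAP. A protocol analysis that never reaches the SAP falls outside that requirement. Elsewhere the SAP does announce a dropped analysis: 7.3.2 says that the planned compliance comparisons will not be done. Nothing similar appears for laboratory shifts.

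The second issue is how to read the change scores. Patients enter with end-stage renal disease and a new kidney then starts to work. A change in potassium, urea nitrogen or haemoglobin from a pre-transplant value carries that recovery as well as any drug effect. The SAP avoids this for creatinine and eGFR by using Day 30, but not for other tests that depend on kidney function.

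**Working it through.** Neither document states a figure on this point, so the main check is a comparison of the texts.

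**1. Planned displays side by side**

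| Display | Protocol 7.5.2 | SAP 7.5.2 and 7.5.2.1 |
|---|---|---|
| Summary statistics by arm and visit | Yes | Yes, for haematology and biochemistry |
| Change from baseline | Yes | Yes, for haematology and biochemistry |
| Normal-range shift table | Yes | None |
| Threshold counts | Not specified | Liver tests only |
| Listings | Yes | Yes (SAP 7.1); urinalysis and coagulation by listing only |

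**2. Which recorded tests are affected**

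Protocol 5.4.3 names twelve items: creatinine, haemoglobin, haematocrit, platelets, white cells, sodium, potassium, urea nitrogen, glucose, urinalysis, tacrolimus trough and HgA1c. Creatinine is partly covered by the eGFR thresholds in SAP 7.4.2, trough levels have their own section (SAP 7.3.3), and urinalysis goes to a listing. That leaves 12 − 3 = 9 quantitative tests with no normal-range count by arm. The liver tests that do get thresholds are not on the protocol's list.

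**3. Whether another table fills the gap**

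Under Protocol 5.5.1 a laboratory abnormality is an adverse event if it causes signs or symptoms, needs intervention, interrupts or stops treatment, or is clinically significant in the investigator's opinion. SAP 7.5.1 tabulates such events by preferred term and arm. That counts the clinically recognised cases. It depends partly on judgement by staff who know the assigned treatment, because the trial is open-label (Protocol 4.4), and it does not count values outside the range that were not judged significant.

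**4. What the pre-transplant baseline does and does not do**

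Let b be the mean pre-transplant value, the same in expectation in both arms by randomisation, and let m1 and m2 be the post-transplant means. Mean change is m1 − b in one arm and m2 − b in the other. The difference between arms is (m2 − b) − (m1 − b) = m2 − m1, so b cancels.

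An illustration with potassium follows. Every value is an assumption, since the documents give none. After transplant a share t of patients has mean 5.8 mmol/L (SD 0.3) and the rest mean 4.4 (SD 0.4). The cut-off is 5.5, and b is 4.7, 5.0 or 5.3.

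- Post-transplant mean = 5.8t + 4.4(1 − t). For t = 6% it is 4.484; for t = 12% it is 4.568.
- Proportion above 5.5 = 0.8413t + 0.0030(1 − t), from standardised cut-offs (5.5 − 5.8)/0.3 = −1 and (5.5 − 4.4)/0.4 = 2.75. For t = 6% it is 5.3%; for t = 12% it is 10.4%.

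| Assumed b | Mean change, t = 6% | Mean change, t = 12% | Difference |
|---|---|---|---|
| 4.7 | −0.216 | −0.132 | 0.084 |
| 5.0 | −0.516 | −0.432 | 0.084 |
| 5.3 | −0.816 | −0.732 | 0.084 |

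Over t = 3% to 20% the proportion above 5.5 runs from 2.8% to 17.1%, while the mean change stays negative throughout (−0.02 to −0.86). Two things follow. A negative change within an arm says little about how many patients are above range. The difference between arms does not depend on b, so what the SAP lacks for comparing arms is the out-of-range count, whichever baseline is used.

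**The case against.** The strongest reply is that this is a descriptive safety display with several substitutes. Absolute values by arm and visit, with SD, median, minimum and maximum, do not use baseline at all. Clinically significant abnormalities are counted as adverse events by arm. eGFR thresholds and a five-point decline are compared by arm, which matters because Protocol 1.3 presents hyperkalaemia as a result of acute renal impairment. Listings remain. All of this stands, and it limits the weight of the point. None of it gives the number of patients outside the normal range by arm for the nine tests.

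The pre-transplant baseline is also not something the SAP introduced. The protocol's schedule of assessments records pre-transplant laboratory values at Day 0, and its statistical section defines no other laboratory baseline. A restored shift table would probably start from the same value. This stands too, and it is why counts that do not depend on baseline should accompany the shift table.

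The silence of the SAP's revision history proves little. It logs changes from version 1 to version 2, and version 1 is not among the documents. If version 1 already lacked the table, there was nothing to log.

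A reader might infer that kidney recovery masks tacrolimus toxicity. The documents do not support that: recovery is common to both randomised arms and the absolute summaries remain. A reader might also infer that the out-of-range proportion would be the more powerful test. Neither document plans a hypothesis test on laboratory data or gives a distribution for any of these tests, so a power argument has no basis here. Nor does the point justify removing the change score, which Protocol 7.5.2 itself requires.

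**Conclusion.** The SAP does not carry out a laboratory analysis that the protocol commits to, and it does not say so. As a result, nine quantitative tests named in Protocol 5.4.3 have no normal-range count by arm. They include potassium and glucose, which bear on risks that the protocol names. The loss is in the readability and objectivity of the safety comparison. The primary analysis, adverse-event reporting and the validity of the comparison between arms are untouched.

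The baseline issue is separate and smaller. For kidney-dependent tests other than creatinine and eGFR, change within an arm cannot be read as a drug effect. This rests on patients having end-stage renal disease before transplant, which the SAP's own baseline tables assume. The size of the recovery in each test is not given in the documents. The potassium figures above are assumed and only show the mechanism.

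This is a low-cost improvement that should be made.

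**What to change.** In SAP 7.5.2:

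- Restore the protocol's normal-range shift table by arm for the recorded haematology and biochemistry tests.
- Add the number and percent of patients below, within and above range, by arm, at each visit and as the worst post-transplant category, using each laboratory's own range.
- Keep change from the pre-reperfusion value. For kidney-dependent tests such as potassium, urea nitrogen and haemoglobin, show change from Day 30 beside it.
- Tabulate urinary protein by arm and visit where it was recorded.
- Record the addition in the revision history. If the sponsor prefers not to restore the shift table, state the omission and the reason.

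The shift table is already promised. The baseline-free counts, the Day 30 change and the urinary protein table are additions to the protocol's plan. The cost is a little programming on data already recorded, provided that local reference ranges were captured. The protocol's commitment presupposes this, but 5.4.3 does not mention ranges.

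Two limits should be footnoted. Ranges and standard-of-care sampling differ between sites. For most tests only the value closest to each visit is recorded, so the worst category is the worst of the recorded values and not of all values drawn.
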